10.1.12 CONFLICT OF INTEREST POLICY

The independence of this study from any actual or perceived influence is critical. Therefore, any actual conflict of interest of persons who have a role in the design, conduct, analysis, publication, financial interest, or any aspect of this trial will be disclosed and managed. Furthermore, persons who have a perceived conflict of interest will be required to have such conflicts managed in a way that is appropriate to their participation in the design and conduct of this trial. The study leadership has established policies and procedures for all study group members to disclose all conflicts of interest and will establish a mechanism for the management of all reported dualities of interest. All persons with direct financial interest in this trial are prohibited to have direct involvement.

10.2 ADDITIONAL CONSIDERATIONS

10.2.1 ETHICS AND RESPONSIBLITY

This study must be conducted in compliance with the protocol, the ICH Guidance for Industry E6(R2) GCP: Consolidated Guidance, the Declaration of Helsinki, IRB requirements, and all applicable national and local regulatory requirements. Investigators must submit all essential regulatory documentation, as required by local and national regulations (including approval of the protocol and ICF by an HHS-registered IRB) to the Sponsor before IP will be shipped to the study site.

10.2.2 AMENDMENT POLICY

Only the Sponsor may modify the protocol. Protocol amendments will be made after consultation between the Sponsor and the Investigator(s). Amendments must be approved by all applicable national and local committees including, but not limited to, the government regulatory authorities and/or regional IRB before implementation. The only exception is when an Investigator considers that a subject may be harmed and immediate action] is necessary. Under these circumstances, approval of the chairman of the IRB, or an authorized designee, must be sought immediately. The Investigator should inform the Sponsor, and the full IRB, no later than 5 working days after the emergency occurs.

Protocol-specified safety reporting requirements must be adhered to independent of any other variables. All amendments that have an impact on subject risk, the study objectives or that require revision of the informed consent document must be approved by the IRB before implementation. Administrative changes to the protocol and/or changes that do not impact subject safety, risk, or

comfort may be implemented prior to IRB approval if local institutional policy permits. A copy of the written approval of the IRB, which becomes part of the essential study documents file, must be given to the study monitor. Examples of amendments requiring such approval are:

- A significant change in the study design
- An increase in the number of invasive procedures to which subjects are exposed
- An addition or deletion of a test procedure

The PI at each study center must sign the Investigator's Agreement page of the amended protocol.

10.3 ABBREVIATIONS

ACQ-7	7-Item Asthma Control Questionnaire
AD	Atopic dermatitis
ADA	Anti-drug antibody
AE	Adverse event
AERD	Aspirin-exacerbated respiratory disease
AUC _[tau]	Area under the concentration-time curve from time 0 to the time of the last quantifiable
	concentration
BMI	Body mass index
ВР	Blood pressure
CFR	Code of Federal Regulations
CI	Confidence interval
CL/F	Apparent clearance
C _{max}	Maximum concentration
CRS	Chronic rhinosinusitis
CRSwNP	Chronic rhinosinusitis with nasal polyposis
СТ	Computed tomography
DNA	Deoxyribonucleic acid
DP	Drug product
DS	Drug substance
DSMB	Data Safety Monitoring Board
ECG	Electrocardiogram
eCRF	Electronic case report forms
EOS	End of study
EOT	End of treatment
ePRO	Electronic patient-reported outcome
EQ-5D	EuroQoL-5D Scale
ETV	Early termination visit
FAS	Full analysis set
FDA	Food and Drug Administration
FEV ₁	Forced expiratory volume
GCP	Good Clinical Practice
GLP	Good Laboratory Practices
GMP	Good Manufacturing Practices
HIPAA	Health Insurance Portability and Accountability Act
HIV	Human immunodeficiency virus
HR	Heart rate
IB	Investigator's Brochure
ICF	Informed consent form
ICH	International Council for Harmonisation of Technical Requirements for Pharmaceuticals
	for Human Use
IgA	Immunoglobulin A
IgE	Immunoglobulin E
INCS	Intranasal corticosteroid
IND	Investigational New Drug Application

IP	Investigational product
IRB	Institutional Review Board
IXRS	Interactive Web Response System
mAb	Monoclonal antibody
MAD	•
	Multiple ascending dose
MedDRA	Medical Dictionary for Regulatory Activities
MFNS	Mometasone furoate nasal spray
MMRM	Mixed effects model with repeated measures National Clinical Trial
NCT	
NMAR	Not missing at random
NP	Nasal polyposis
NPIF	Nasal peak inspiratory flow
NPS	Nasal Polyp Score
OCS	Oral corticosteroids
OHRP	Office for Human Research Protections
PI	Principal Investigator
PK	Pharmacokinetics
PP	Per protocol
Q4W	Every 4 weeks
Q8W	Every 8 weeks
QC	Quality control
QoL	Quality of life
SAD	Single ascending dose
SAE	Serious adverse event
SAP	Statistical Analysis Plan
SC	Subcutaneous(ly)
SF-36	Short Form 36 Health Survey
SNOT-22	Sino-Nasal Outcome Test
SoA	Schedule of Activities
SOC	System organ class
SOP	Standard Operating Procedure
t _{1/2}	Apparent terminal half-life
TCA	Tricyclic antidepressant drugs
TEAE	Treatment-emergent adverse event
ТВ	Tuberculosis
Th2	T helper type 2
t _{max}	Time of maximum concentration
UP	Unanticipated problem
UPSIT	University of Pennsylvania Smell Identification Test
US	United States
VAS	Visual Analogue Scale
Vd/F	Apparent volume of distribution
WOCBP	Woman of childbearing potential
SAP SC SF-36 SNOT-22 SOA SOC SOP t _{1/2} TCA TEAE TB Th2 t _{max} UP UPSIT US VAS Vd/F	Serious adverse event Statistical Analysis Plan Subcutaneous(ly) Short Form 36 Health Survey Sino-Nasal Outcome Test Schedule of Activities System organ class Standard Operating Procedure Apparent terminal half-life Tricyclic antidepressant drugs Treatment-emergent adverse event Tuberculosis T helper type 2 Time of maximum concentration Unanticipated problem University of Pennsylvania Smell Identification Test United States Visual Analogue Scale Apparent volume of distribution

10.4 PROTOCOL AMENDMENT HISTORY

Version	Date	Description of Change	Brief Rationale
Original Protocol	21 September 2018		
Amendment 1	15 February 2019	Administrative corrections, updated Inclusion/exclusion criteria, clarified procedures. See Summary of Changes for complete summary.	Improving patient safety, aligning criteria in patients enrollment, and improving protocol based on input provided by DSMB and participating clinical Investigators with strong patient management experience.
Amendment 2	15 August 2019	Updated inclusion/exclusion criteria; clarified procedures; updates on statistical considerations, dropout rate and sample size; administrative corrections. See Summary of Changes for complete summary.	Providing clarification, improving patient safety and improving protocol based on input provided by participating clinical Investigators with strong patient management experience.
Amendment 3	06 February 2020	Corrected inconsistencies in objectives and endpoints listed throughout the document and corrected administrative errors.	The synopsis, Section 3, and statistical sections were not consistent for the objectives and endpoints listed.

APPENDIX A: PROHIBITED MEDICATIONS AND THERAPIES DURING THE COURSE OF THE STUDY

Excluded medications/therapies are listed below. The use of an excluded medication/therapy is a protocol violation and must be recorded in the eCRF. **The following medications will not be permitted during the study:**

- Biologics, monoclonal antibodies including but not limited to: anti-immunoglobulin E (IgE) therapy (omalizumab), anti-IL-5 therapy (mepolizumab, benralizumab) anti-IL-4/13 (dupilumab)
- Any immunosuppressive treatment including but not limited to: methotrexate, cyclosporine, mycophenolate, tacrolimus, gold, penicillamine, sulfasalazine, hydroxychloroquine, azathioprine, cyclophosphamide
- Aspirin or nonsteroidal anti-inflammatory (NSAID) in patients with hypersensitivity to aspirin or NSAID
- Systemic corticosteroid
- Decongestion (topical or systemic) is not allowed, except before endoscopy
- Long term use of systemic antibiotics (for 2 weeks or more)
- Lipoxygenase inhibitors
- Use of intranasal medication that could interfere with the symptoms of diseases are prohibited (this includes but is not limited to: chronic use of INCSs, antihistamines, nasal atropine, ipratropium bromide, nasal cromolyn)
- Chronic use of nasal antihistamines within 8 weeks of Screening is prohibited (however acute episodic use within 8 weeks of Screening is permitted. Oral antihistamines and nasal saline are permitted both during Screening and while on-study).
- Polypectomy (allowed as part of medical history up to 3 months prior to randomization)

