To assess improvement in Quality of Life (QoL) in subjects with CRSwNP treated with etokimab compared to placebo following a 16-week treatment period	 QoL: 36-item Short Form Health Survey (SF-36) European QoL scale (EQ-5D) Patient-related rhinosinusitis symptoms severity using a visual analogue scale (VAS) Number of nocturnal awakenings 	To assess the effect of etokimab on the patients' symptoms and quality of life
To assess other effects of etokimab compared to placebo in subjects with CRSwNP following a 16-week treatment period	 Percent change from baseline to Week 16 in sinus opacification as assessed by CT scan using Lund-Mackay score Change from baseline to Week 16 in nasal peak inspiratory flow (NPIF) Change from baseline to Week 16 in NPS in subjects with comorbid asthma Change from baseline to Week 16 in Sino-Nasal Outcome Test (SNOT-22) scores in subjects with comorbid asthma Percent change from baseline to Week 16 in 3-dimensional volumetric measurement of the maxillary sinus as assessed by CT scan Change from baseline to Week 16 in forced expiratory volume (FEV₁) (overall and in subgroup with asthma) Change from baseline to Week 16 in FEV₁ percent of predicted (overall and in subgroup with asthma) 7-Item Asthma Control Questionnaire (ACQ-7) in asthma subgroup Reduction of eosinophils (blood eosinophil count) from baseline (Day 1 pre-dose) to Week 16 	All other efficacy endpoints have been recategorized as exploratory endpoints Additional measures of treatment response are established methods to characterize the clinical impact of treatment Patient-reported outcomes specific to CRSwNP provide additional evidence to support the physician assessment of outcome

OBJECTIVES	ENDPOINTS	JUSTIFICATION FOR ENDPOINTS
	 Time to study treatment discontinuation Incidence of treatment discontinuation due to need for oral corticosteroids (OCS) or nasal polyp surgery Change in Nasal Polyp Resource Questionnaire from baseline to Week 16 	

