6.5.1 RESCUE MEDICINE

Use of rescue medication (eg, systemic corticosteroid) is not permitted in this study (except MFNS as supplied per protocol). If a subject receives systemic rescue treatment the subject will be discontinued from the study and should return for a final Early Termination Visit (ETV) within 30 days from last dose. Study procedures should be completed according to the ETV/EOS per Section 1.3. In the case of ongoing AEs/SAEs, the subject should be followed up until it has resolved or stable outcome or subject is lost to follow-up. The date and time of rescue medication administration, as well as the name and dosage regimen of the rescue medication, must be recorded into the eCRF/study database by study center personnel.

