7 STUDY INTERVENTION DISCONTINUATION AND PARTICIPANT DISCONTINUATION/WITHDRAWAL

7.1 DISCONTINUATION OF STUDY INTERVENTION

Study treatment can be interrupted temporarily in case of an AE as per the Investigator's discretion. The medical monitor should be informed. Restarting study treatment at the next scheduled administration study visits can be done after discussion with the medical monitor.

In the case of discontinuation from study treatment the subject should return for an ETV within 30 days from last dose and will be encouraged to complete their remaining clinic visits as planned. Study procedures should be completed according to the (ETV)/(EOV) per Section 1.3. Ongoing AEs/SAEs, the patient should be followed up until it has resolved or stable outcome or subject is lost to follow-up.

If a clinically significant finding is identified (including, but not limited to changes from baseline) after enrollment, the Investigator or qualified designee will determine if any change in participant management is needed. Any new clinically relevant finding will be reported as an AE.

In case of early withdrawal from the study, the subject will be required to return as noted above for ETV. Procedures should be completed in accordance with the SoA (see Section 1.3) Week 24/ETV.

If an ETV occurs within 7 days of the previous visit lab re-draws are not required unless clinically significant labs were noted.

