7.2 PARTICIPANT DISCONTINUATION/WITHDRAWAL FROM THE STUDY

Subjects are free to withdraw from participation in the study at any time upon request.

An Investigator must discontinue or withdraw a subject from the study and follow for safety for the following reasons:

- Any subject becomes pregnant or indicates they are planning to become pregnant during the study
- Any LFT abnormality that meets the following criteria require discontinuation:
 - If a subject has at any time post-initial dose an AST or ALT >5-8x ULN for more than 2 weeks, discontinue dosing; or
 - AST or ALT >8x ULN, irrespective of duration discontinue dosing; or
 - o Concurrent AST or ALT >3x ULN and total bilirubin >2x ULN discontinue dosing.

An Investigator may discontinue or withdraw a subject from the study for the following reasons:

- Significant study intervention noncompliance (eg, failure to follow study procedures or to keep follow-up appointments)
- If any clinical AE, laboratory abnormality, or other medical condition or situation occurs such that continued participation in the study would not be in the best interest of the subject
- Disease progression which requires discontinuation of the study intervention
- If the subject meets an exclusion criterion (either newly developed or not previously recognized) that precludes further study participation

If the subject withdraws consent and discontinues from the study, the Investigator will attempt to determine the reason for discontinuation and record the reason in the subject's study records and on the eCRF. If a subject withdraws consent because of an AE, that AE should be indicated as the reason for withdrawal. In the event of early discontinuation, the subject should be asked to return to the study center to complete the assessments specified in the ETV.

If at any time during the study, the investigator determines that it is not in the best interest of the subject to continue, the subject will be discontinued from participation. The Investigator can discontinue a subject at any time if medically necessary. Appropriate documentation in the subject's study record and eCRF regarding the reason for discontinuation must be completed. Prior to discontinuing a subject from study participation, the Investigator will discuss his/her intentions with the medical monitor or designee.

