9.4.2.1.1 FIRST CO-PRIMARY ENDPOINT

The first co-primary endpoint is the change from Baseline to Week 16 in bilateral endoscopic NPS while on treatment.

Baseline endoscopic NPS is the sum of the left and right nasal polyposis score at the randomization visit. The NPS is also measured every 4 weeks during treatment and at end of treatment (Week 16). A general linear MMRM using change from baseline in NPS scores at Weeks 4, 8, 12, and 16 as response, stratification factor, treatment group as fixed effect (3 levels), treatment by stratification factor, and treatment by time interaction as fixed effects, Baseline (Day 1) NPS score as fixed continuous covariate, and subject as a random effect, will be used to obtain least squares means at EOT, to compare the etokimab treatment arms with the placebo arm.

No imputation of data for missing data due to treatment discontinuation will be implemented in the primary analysis. Comparison of the treatment arms will be based on the Week 16 least squares means of the treatment arms. An unstructured covariance matrix will be assumed and estimated in order to obtain associated standard errors for least squares means and to carry out the treatment comparisons. In case of convergence problems for the maximum likelihood estimates, other covariance structures with fewer parameters may be sought from the range of options provided in SAS PROCEDURE MIXED.

Comparison of each treatment arm with placebo will be based on the Week 16 least squares means obtained from the MMRM, where missing data due to treatment discontinuation are regarded as missing at random. Testing will be conducted in a hierarchical manner such that the comparison of the etokimab every 4 weeks treatment arm versus placebo will be conducted first. If the results of the comparison of the etokimab every 4 weeks treatment arm versus placebo are statistically significant, the etokimab every 8 weeks treatment arm will be compared to placebo. The p-value for the comparison will be obtained and compared to the significance level of 5%. An associated 2-sided 95% confidence interval will be obtained for the active minus placebo change from baseline to week 16 in the NPS for each treatment arm tested. No further adjustment will be made for testing each dosing regimen with placebo.

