8.2.2. Responder Analysis: Week 16 NPS Score Decrease of ≥1 from Baseline

One of the (co)primary endpoints is the change from baseline in NPS score at Week 16. For this variable, a responder may be defined as a subject whose NPS score at Week 16 decreased from baseline by at least 1.0. If

the subject did not make it to Week 16, or if the subject did not achieve an NPS score reduction ≥ 1 , the subject will be deemed a "Non-responder" (Response='No').

Summary statistics for each treatment group will include the number (n) and percentage (%) of subjects who responded, and an exact confidence interval for the % responders.

A logistic regression will be employed with terms for treatment (3 levels: 1=Placebo, 2=Eto Q8W, 3=Eto Q4W), baseline as a continuous covariate, and stratification factor (asthma comorbidity:1=Yes, 0=No).

Using the logistic regression model, for each comparison of the etokimab groups with the Placebo group, the estimated odds ratio for the etokimab versus placebo odds of response, a 95% Confidence Interval for the odds ratio, and the p-value for that comparison will be displayed in the summary table.

It is expected that treatment with etokimab should lead to a greater odds of response vs. not responding, when compared to the Placebo group. A statistically significantly greater odds ratio for the etokimab vs. placebo group comparison will be taken as evidence of efficacy in favor of etokimab.

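### An NPS fall after on-study polyp surgery counts as a response in both NPS response endpoints, and the primary NPS analysis is contradictory on whether such scores are used.

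*Protocol*

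**What the plan says.** **Status of surgery.** Protocol Appendix A lists it among the therapies not permitted during the study: "Polypectomy (allowed as part of medical history up to 3 months prior to randomization". The appendix states one consequence: "The use of an excluded medication/therapy is a protocol violation and must be recorded in the eCRF".

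**Withdrawal.** The mandatory list in Protocol 7.2 opens with "An Investigator must discontinue or withdraw a subject from the study and follow for safety for the following reasons" and contains pregnancy (or plans for it) and liver-function criteria. Protocol 6.5.1 adds one more trigger: "If a subject receives systemic rescue treatment the subject will be discontinued from the study". Surgery is in neither. Other withdrawals under 7.2 are at the investigator's discretion.

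**Surgery is foreseen.** An exploratory endpoint in Protocol Section 3 is "Incidence of treatment discontinuation due to need for oral corticosteroids (OCS) or nasal polyp surgery". Under Protocol 7.1, a subject who stops treatment returns for an early termination visit and "will be encouraged to complete their remaining clinic visits as planned".

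**Response endpoints.** SAP 8.2.1 counts the first fall of at least 1 point in NPS and censors only subjects with no such fall on study. It is the first endpoint in the secondary hierarchy of SAP 8.2. SAP 8.2.2 says "a responder may be defined as a subject whose NPS score at Week 16 decreased from baseline by at least 1.0"; a subject is a non-responder only for not reaching Week 16 or for falling short of that reduction.

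**Primary endpoint.** Protocol 9.4.2.1.1 defines it as "change from Baseline to Week 16 in bilateral endoscopic NPS while on treatment" and puts NPS values seen after treatment discontinuation in an optional sensitivity analysis. SAP 8.1.1.1 labels the estimand treatment policy, yet in the same sentence restricts it to on-treatment values.

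**The concern.** NPS grades polyp size (Protocol Appendix D), which is the tissue that surgery removes. A subject whose disease led to an operation can therefore show a lower score for a reason unrelated to study drug, and the two response rules read that score as success. Time to first response comes first in the hierarchy, so its result decides whether the later secondary endpoints can be interpreted for significance.

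With 27 evaluable subjects planned per arm, one or two such records are visible in the result. If the handling is chosen after treatment codes are known, it is open to challenge whichever way it goes.

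**Working it through.** **1. Which analyses use a post-surgery NPS?**

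- *Time to first response (SAP 8.2.1).* The rule looks only at the score. An operated subject with no earlier response and a later score at least 1 point below baseline becomes an event instead of a censored record.
- *Week 16 responder (SAP 8.2.2).* The rule again looks only at the score. If the subject attends Week 16 and is at least 1 point below baseline, the subject is a responder.
- *Primary MMRM, surgery leads to stopping treatment.* The on-treatment wording in Protocol 9.4.2.1.1 and SAP 8.1.1.1 leaves the score out. The treatment-policy label in SAP 8.1.1.1 keeps it in.
- *Primary MMRM, surgery after the Week 12 dose.* Week 12 is the last planned dose, so no dose remains to be stopped. The SAP does not define on-treatment for efficacy. Its exposure convention (SAP 10.1) adds 28 days to the last dose, and Day 85 + 28 = Day 113, the Week 16 target day. The score stays in under both readings.

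**2. The plan's own power.** Inputs from Protocol 9.2 and SAP 3.6: difference 1.3, SD 1.5, 27 per arm, two-sided 5%.

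SE = 1.5 × √(2/27) = 0.408, and 1.3 / 0.408 = 3.18. Power is 87.8% with the noncentral t distribution (89.0% with the normal approximation). The plan states about 87%, so the figure reproduces.

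**3. Responder rate.** One subject is 1/27 = 3.7 percentage points of an arm (1/33 = 3.0 if all randomized subjects count). For scale, assume normal changes with SD 1.5 and means of 0 on placebo and -1.3 on etokimab. The responder rates are Φ(-1/1.5) = 25% and Φ(0.3/1.5) = 58%, an odds ratio of 4.1. Suppose k placebo subjects who would otherwise not respond are operated on and score as responders:

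| k of 27 | Placebo rate | Odds ratio |
|---|---|---|
| 0 | 25% | 4.1 |
| 1 | 29% | 3.4 |
| 2 | 33% | 2.8 |
| 3 | 36% | 2.4 |

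A rule that scores them as non-responders leaves 25% and 4.1.

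**4. Primary comparison, only if post-surgery scores enter.** The documents give neither a surgery rate nor a post-surgery NPS. Assume each operated subject scores g = 2 to 4 points lower than otherwise.

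With k operated on placebo, the difference is 1.3 - k × g / 27. The placebo variance is 1.5² + p(1 - p)g², with p = k/27.

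| k of 27 (placebo) | Difference, g = 2 to 4 | Power |
|---|---|---|
| 0 | 1.30 | 88% |
| 1 | 1.23 to 1.15 | 83% to 74% |
| 2 | 1.15 to 1.00 | 77% to 58% |
| 3 | 1.08 to 0.86 | 70% to 42% |

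The same event in an etokimab arm works the other way: one operated subject raises the apparent difference to between 1.37 and 1.45.

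**The case against.** **The primary analysis is partly protected.** A reader might infer that no rule anywhere excludes later scores, so that every operated subject counts as improved in the primary model. The documents do not support that. Protocol 9.4.2.1.1 and the data clause of SAP 8.1.1.1 both limit the primary analysis to on-treatment values. A subject who stops drug because of surgery therefore meets conflicting text, not silence. This objection stands for the MMRM. It does not reach the two response endpoints or a subject operated on after the last dose.

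**Other safeguards exist.** The investigator may withdraw a subject for disease progression that requires stopping, or for a newly met exclusion criterion (planned surgery is exclusion 22). Systemic rescue given alongside surgery would also trigger withdrawal. These are discretionary or depend on another event, so they limit the problem without removing it.

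**Per-protocol analysis.** A major deviation affecting efficacy removes the subject from that set, and Protocol 9.4.2 repeats the co-primary analyses there without condition. SAP 8.1.1.3, however, repeats the NPS analysis only if the two sets differ by more than 10 subjects. The analysis is supplementary, and it drops the subject instead of recording a failure.

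**Response is not automatic.** It needs surgery before the endoscopy, continued attendance, a readable image and a score at least 1 point below baseline. That is correct.

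**Size and direction.** A reader might take a more extreme case, such as an operated placebo subject going from 6 to 1, which gives a difference of 1.12 and power of 71%. Nothing in the documents supports that change. Nor do they show that surgery is likelier on placebo, so a bias against etokimab cannot be assumed.

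**Conclusion.** The concern holds for the two NPS response endpoints: as written, they count a surgically lowered score as a response in the full analysis set. For the primary NPS analysis it holds in a narrower form. The estimand text contradicts itself for subjects who stop treatment because of surgery, and a subject operated on while still on treatment is excluded under neither reading.

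The responder effect is about 3.7 percentage points of an arm of 27 per operated subject who would otherwise not respond. If post-surgery scores enter the model, one operated placebo subject lowers power from 88% to between 83% and 74%. Both figures rest on assumed surgery counts, and the second also on an assumed shift of 2 to 4 points. If no surgery occurs, nothing changes. Surgery on placebo dilutes the effect and surgery on etokimab inflates it.

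**What to change.** - **SAP 8.2.1:** state that an NPS fall first seen after nasal polyp surgery is not an event.
- **SAP 8.2.2:** state that a subject with nasal polyp surgery before the Week 16 endoscopy is a non-responder.
- **SAP 8.1.1.1:** reconcile the treatment-policy label with the on-treatment wording and with Protocol 9.4.2.1.1. State before unblinding whether post-surgery NPS enters the MMRM, and run the other handling as a sensitivity analysis. Several strategies are defensible here, including treating the scores as missing or carrying forward a pre-surgery value. The documents do not settle which is right, but one must be named.

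The cost is SAP wording and one derivation flag. The data should already be on file: Appendix A requires the violation in the eCRF, and the Schedule of Activities defines concomitant therapy to include nonpharmacologic therapy. No dose, visit, withdrawal or other clinical rule changes.
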